7. PREMATURE INTERRUPTION OF THE INVESTIGATION

8. TRIAL REGISTRATION

9. GLOSSARY

10. ATTACHMENTS TO THE INVESTIGATION PLAN

11. BIBLIOGRAPHY

1. SYNOPSIS

TITLE	"Evaluation of the performance and safety of a Type I collagen-based medical device (MD-Small Joints Collagen Medical Device) in the treatment of rhizarthrosis. "SMAGENART Pilot Study"
STUDY DESCRIPTION	Multicenter pilot study based on a One sample design. The variables will be assessed at 4 different time points: at baseline (time T0), after 3 weeks (T3s), after 6 weeks (T6s), and after 16 weeks (T16s/FU), i.e., after 10 weeks from the end of the infiltrative treatment.
OBJECTIVES	The purpose of this research is to evaluate, using the Visual Analogue Scale (VAS), the performance of an intra-articular and peri-articular treatment with a collagen-based medical device in terms of pain reduction and joint function recovery in subjects affected by symptomatic rhizarthrosis. The safety of the treatment will also be assessed.
PRIMARY ENDPOINT	The primary endpoint will consist of the evaluation, through the Visual Analogue Scale (VAS), of the performance of MD-Small Joints Collagen Medical Device in reducing pain associated with trapeziometacarpal osteoarthritis, at time T6 weeks (T6s) compared to T0. A reduction in VAS score of at least 30% is considered clinically significant.
POPULATION	A total of 42 subjects responding to the selection criteria will be progressively enrolled at the Clinical Investigation Centers involved.
SELECTION CRITERIA	
Inclusion Criteria:
 
• Male and female subjects aged between 18 and 75 years.• Subjects with clinically diagnosed symptomatic rhizarthrosis confirmed radiographically (Stage I and II according to the classification of Eaton and Littler).• Subjects with a VAS score ≥ 5.• Subjects with joint pain for at least 1 month.• Subjects not using trapeziometacarpal orthotic devices.• Subjects who agree not to take analgesics within 24 hours before the scheduled visits.• Subjects capable of understanding and signing the Informed Consent.

	
Exclusion Criteria:
 
• Subjects with rheumatological pathology involving the hands.• Subjects who have undergone surgery on the hand affected by pathology.• Subjects who have received HA infiltrations in the trapeziometacarpal joint in the last 3 months.• Subjects who have taken anti-inflammatory drugs in the last 7 days and/or corticosteroids in the last 30 days.• Subjects undergoing physical therapy such as X-ray therapy, Tecar therapy, shock waves, laser therapy, ultrasound therapy in the last 3 months.• Subjects with neoplastic pathology.• Subjects with systemic infections.• Subjects with uncontrolled diabetes.• Subjects with neurological pathologies that may affect active participation in the study.• Subjects with coagulopathies or taking anticoagulants (vitamin K antagonists, heparin).• Subjects undergoing immunosuppressive therapy.• Subjects using drugs or abusing alcohol.• Subjects with allergy to porcine collagen.• Subjects who are pregnant or breastfeeding.• Subjects participating in other clinical studies during the same period.• Subjects unable to cooperate or for whom poor compliance is expected.• Any condition that, in the opinion of the investigator, recommends the subject's exclusion.
STUDY PHASE	Phase IV post market
NUMBER OF SITE	2 Clinical Investigation Centers
DESCRIPTION OF THE INVESTIGATIONAL DEVICE	The MD-Small Joints Collagen Medical Device is an injectable medical device composed of Type I porcine collagen. Each unit of the device contains 100µg of collagen per 2ml volume.
DURATION OF THE STUDY	The entire clinical investigation will span over 8 months. It comprises a 4-month period for subject selection and recruitment, followed by a

	4-month period for treatment and observation.
DURATION OF THE STUDY FOR EACH SUBJECT	The duration of the study for each subject will be 4 months.

2. LISTA DELLE ABBREVIAZIONI

AE	Adverse Event
ALP	Abductor Pollicis Longus "
DASH	Disability of the Arm, Shoulder and Hand
E-CRF	"Electronic Case Report Form."
FIHOA	Functional Index for Hand OsteoArthritis
FU	Follow Up
GCP	Good clinical practice
HA	Hyaluronic acid
ICH	International Council for Harmonisation of Technical Requirements for Pharmaceuticals for Human Use
LIM	Intermetacarpal Ligament
MD	Medical Device
SAE	Serious Adverse Event
TM	Trapeziometacarpal Joint
VAS	Visual Analogue Scale

3. INTRODUCTION

3.1 Overview of the Functional Anatomy of the Trapeziometacarpal Joint

The trapeziometacarpal joint (TM) can be considered a "saddle" or reciprocally interlocking joint, with movements primarily occurring in two planes: anterior/posterior movement on the sagittal plane and abduction/adduction on the frontal plane [1;2].

Additionally, the relatively lax joint capsule allows axial rotation of the metacarpal around its longitudinal axis [2]. This third degree of articulation enables thumb opposition movement in bi-digital grips. The most significant movement is the pinch grip between the thumb and index finger, which can be distinguished as terminal, more refined and precise for securely grasping small objects, and sub-terminal, more recurrent and instinctive, where the thumb and index finger oppose with the palmar aspect of the fingertip and can grip objects of various sizes. In this latter grip, significant radial tension force is created on the metacarpal base, stretching the joint capsule and the intermetacarpal ligament over time, making them increasingly lax. This laxity results in joint instability, causing radial subluxation of the metacarpal and joint degenerative processes [1;3].

The genesis of rhizarthritis lies precisely in TM instability, which can be primary or secondary (traumatic). In ligamentous laxity, instability is due to excessive range of motion, where the palmar ligament, limiting metacarpal hyperextension, and the intermetacarpal ligament (LIM), stretched between the base of the first and second metacarpal bones, which normally limits abduction movement of the first metacarpal bone, play a key role. Its relaxation is the basis for external subluxation of the base of the first metacarpal bone, leading to incongruity of the joint surfaces and initiating joint instability [2;3].

Another recognized and considered frequent cause is instability due to the absence of insertion of the abductor pollicis longus (APL) on the trapezium. In cases where the APL has a double distal insertion on the trapezium and the base of the first metacarpal bone, with each contraction of the APL, the entire thumb-metacarpal-trapezium column moves into abduction, maintaining normal trapeziometacarpal joint relationships. Conversely, if the insertion on the trapezium is absent, all abduction force is exerted on the base of the first metacarpal bone, causing significant subluxation tension with a deleterious effect on the TM cartilage [4].

3.2 Osteoarthritis of the Trapeziometacarpal Joint

The term rhizarthritis refers to the arthritic process involving the TM joint. It is a condition that affects approximately 20% of the population over 50 years of age and is more common in females (ratio 4:1), typically manifesting around menopause. In 50% of cases, symptoms are bilateral [5; 6; 7]. The repeated grasping of small objects results in radial stress on the base of the first metacarpal bone,

with a significant increase in the destabilizing force transmitted at this level and progressive laxity of the capsulo-ligamentous apparatus [8; 9]. Consequently, joint laxity, altered load distribution, cartilage deterioration, and the onset of pain occur [1]. Disease progression is accompanied by a reduction in the strength of the thenar muscles and progressive subluxation of the TM joint, which in advanced stages can lead to complete dislocation of the base of the first metacarpal bone. As a compensatory phenomenon, the first ray metacarpophalangeal joint tends towards hyperextension in an attempt to preserve grip function: the thumb assumes a characteristic deformation called "Z-thumb" [12]. From a clinical standpoint, patients present with localized pain at the base of the thumb, exacerbated by active radial abduction and/or passive rotation-opposition movements [13], resulting in functional limitation and a decline in quality of life [10; 11].

The diagnosis of rhizarthrosis is clinical, confirmed by the presence of bone deformities and the above-described signs and symptoms. Radiographic examination allows instrumental staging of the disease. Eaton and Glickel first described a classification of the pathology based on the appearance of the joint in standard radiographic projections and under stress [14; 5]. The classification most commonly used today is the Eaton-Littler classification modified by Brunelli, which, in addition to the radiographic picture, also considers the clinical-functional aspect [5].

In the first stage of rhizarthrosis, treatment is usually conservative; in the second stage and early third stage, surgical treatment may be indicated using techniques for biological stabilization of the joint [3; 15; 16]. In Eaton's third stage, prosthetic joint replacement may also be indicated, while in the fourth stage, the current trend is to perform a suspension arthroplasty surgical intervention [17].

Multiple alternatives have been proposed in the conservative management of symptomatic rhizarthrosis, with varying degrees of evidence and efficacy. These include:

Orthoses: In a recent meta-analysis, orthosis use has been shown to be beneficial in reducing moderate/severe pain in the medium term (3-12 months) and improving function, and can avoid surgery in some patients [18; 19]. Additionally, they act as an insulating layer, which can help reduce worsening symptoms related to cold. For some patients, taping may be a good alternative [20].

Motor rehabilitation: Treatments performed by therapists experienced in hand pathology lead to significant improvement in pain and function [21]. Specific manual exercises help increase grip strength, reduce pain, and improve thumb joint mobility [22].

Pharmacological therapy: The American College of Rheumatology in 2012 and the European League against Rheumatism recommended the use of one or more of the following drugs for patients with hand osteoarthritis: topical capsaicin, oral NSAIDs, including selective COX2 inhibitors, and oral chondroitin sulfate. There is no literature evidence of the superiority of one specific anti-inflammatory treatment over another [23; 24].

Infiltrative therapy: Corticosteroid injections into the trapeziometacarpal joint can result in pain reduction and functional improvement, but mainly in the short term and with significant side effects [25; 26; 27]. Hyaluronic acid injections represent an alternative to anti-inflammatory infiltrative therapy [28] and result in reduced resting pain with lasting benefit from 4 to 12 weeks [29].

3.3 Clinica Clinical Investigation Rationale

Collagen is a structural protein biopolymer composed of three polypeptide chains wound together to form a right-handed triple helix. Its structure, characterized by the presence of glycine every third residue, a high content of proline and hydroxyproline, is stabilized by interchain hydrogen bonds and electrostatic interactions, which confer high mechanical strength, incompressibility, and, simultaneously, extensibility, plasticity, and flexibility to the molecules, making tissues abundant in collagen particularly resistant to stress and load [30].

In humans, collagen is particularly present in the skin, subcutaneous tissue, cartilage, bone, joint capsule, tendons, muscles, and ligaments [31; 32; 33]. Growing evidence supports the infiltrative use of type I collagen in the treatment of musculoskeletal pathologies [34]. In particular, the intra-articular and peri-articular use of collagen has been proposed in the treatment of osteoarthritis of various body districts with the aim of limiting joint hypermobility, stabilizing the structure of joint and peri-articular components, reducing pain, and consequently improving function. Several clinical studies have demonstrated how its infiltrative intra-articular use, characterized by a series of 5 injections spaced one week apart, was able to determine pain reduction and improvement of functionality in different cases of knee and hip osteoarthritis [35; 36; 37; 38; 39]. Regarding the conservative management of symptomatic rhizarthrosis, some studies, although on limited case series, have shown how the use of type I collagen at the joint and peri-articular level in this condition is able to control painful symptoms, improve functionality, and reduce joint instability [40].

Recently, Randelli F. et al. studied the in vitro effects on tenocytes induced by type I porcine collagen (MD-Tissue Collagen Medical Device). In vitro results seem to demonstrate that this medical device can induce proliferation and migration of tenocytes and synthesis, maturation, and secretion of type I collagen, favoring tendon repair [41].

Randelli F. et al. also demonstrated the predominantly mechanical activity of MD-Tissue Collagen Medical Device, which is able to induce modifications of the morpho-functional properties of tenocytes [42].

In this Clinical Investigation, the performance and safety of use of an injectable medical device based on type I porcine collagen called MD-Small Joints Collagen Medical Device in the treatment of symptomatic rhizarthrosis will be investigated.

4. SCIENTIFIC REQUEST

4.1 Research Title

"Evaluation of the Performance and Safety of a Type I Collagen-Based Medical Device (MD-Small Joints Collagen Medical Device) in the Treatment of Rhizoarthritis: The SMAGENART Pilot Study."

4.2 Research Objective

The aim of this research is to evaluate, using the Visual Analogue Scale (VAS), the Disability of the Arm, Shoulder and Hand (DASH) questionnaire, the Functional Index for Hand Osteoarthritis (FIHOA) questionnaire, and the Pinch Strength Test, the performance of an intra-articular and peri-articular treatment with a collagen-based medical device in terms of pain reduction and recovery of joint function in subjects with symptomatic rhizoarthritis. The safety of the treatment will also be assessed.

4.3 Study Design

This multicenter pilot clinical investigation will be based on a One Sample design. The variables will be assessed at 4 different time points: baseline (time T0), after 3 weeks (T3s), after 6 weeks (T6s), and after 16 weeks (T16s/FU), which is 12 weeks after the end of the infiltrative treatment.

4.4 Duration of Investigation

The total duration of the investigation will be 8 months. It is expected that the selection and recruitment of subjects will take 4 months, followed by a treatment and observation period of 16 weeks (Figure 1).

[figure not shown]

Fig.1 Study Clinical Design

4.5 Participant Population

A total of 42 subjects with thumb carpometacarpal osteoarthritis will be enrolled. The recruitment phase will not be closed until the number of subjects specified in the Clinical Investigation Plan is reached.

Only subjects who meet the following criteria will be included:

- Belonging to the Clinical Investigation Centers.

- Meeting the inclusion criteria and not presenting exclusion criteria.
- Having dated and signed the Informed Consent.

4.6 Enrollment

Enrollment will commence only after approval of the Clinical Investigation Plan by the relevant Territorial Ethics Committees and notification of the study to the Ministry of Health.

Enrollment will involve subjects with thumb carpometacarpal osteoarthritis who are eligible according to the selection criteria. Diagnosis will be performed by the Principal Investigator of each Clinical Investigation Center through clinical and radiological examination. Eligible subjects will be briefed by the Principal Investigator or Co-Investigators on the rationale of the Clinical Investigation and the planned procedures. Consent to participate in the study will then be requested.

4.7 Selection Criteria

4.7.1 Inclusion Criteria:

- Male and female subjects aged between 18 and 75 years;
- Subjects with clinically diagnosed symptomatic thumb carpometacarpal osteoarthritis confirmed radiographically (stages I and II according to Eaton and Littler's classification);
- [N.B. in case of bilateral symptomatic thumb carpometacarpal osteoarthritis, treatment can be unilateral only, at the level of the thumb carpometacarpal joint that is more affected at the time of enrollment].
- Subjects with a VAS score ≥ 5 ;

[The request for pain intensity (VAS) from the patient should refer to moments of hand use, not at rest!]

- Subjects with joint pain for at least 1 month;
- Subjects not using thumb carpometacarpal orthotic devices;
- Subjects agreeing not to take analgesics within 24 hours before the scheduled visits;
- Subjects capable of understanding and signing the Informed Consent.

4.7.2 Exclusion Criteria

- Subjects with rheumatological conditions involving the hands;
- Subjects who have undergone hand surgery for the affected pathology;
- Subjects who have received HA injections in the thumb carpometacarpal joint in the last 3 months;
- Subjects who have taken NSAIDs in the last 7 days and/or corticosteroids in the last 30 days;
- Subjects undergoing physical therapy such as X-ray therapy, Tecar therapy, shock wave therapy, laser therapy, ultrasound therapy in the last 3 months;
- Subjects with neoplastic pathology;

- Subjects with systemic infections;
- Subjects with uncontrolled diabetes;
- Subjects with neurological conditions that may affect active participation in the study;
- Subjects with coagulopathies or taking anticoagulants (vitamin K antagonists, heparin);
- Subjects undergoing immunosuppressive treatment;
- Subjects using drugs or abusing alcohol;
- Subjects allergic to porcine collagen;
- Female subjects who are pregnant or breastfeeding;
- Subjects participating in other clinical studies during the same period;
- Subjects unable to cooperate or for whom poor compliance is expected;
- Any condition that, in the investigator's judgment, recommends the subject's exclusion.

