4.9.2 Visit Schedule

Baseline (T0): Enrollment

During routine clinical practice, the Investigators participating in the Clinical Investigation will select subjects diagnosed with symptomatic thumb carpometacarpal osteoarthritis. The Principal Investigator will be responsible for the correct clinical diagnosis, also utilizing the instrumental exams specified in the Investigation Plan. Subjects meeting the selection criteria will be identified. After thoroughly explaining the purposes, objectives, and procedures outlined in the Investigation Plan, the subject will be invited to participate in the Investigation. The selected subject will be invited to review the information sheet and date and sign the Informed Consent and Personal Data Processing Consent

form. Female subjects must provide evidence of a negative pregnancy test to be enrolled. The examination will then proceed, along with the collection of information required by the electronic Data Collection Form (e-CRF) appropriately prepared.

This will be followed by:

- VAS assessment;
- DASH assessment;
- FIHOA assessment;
- Pinch Strength Test assessment using a dynamometer.

The first intra/peri-articular infiltration of MD-Small Joints Collagen Medical Device (see § 4.12) will then be performed, evaluating any Adverse Events in the moments following administration. Any previous or ongoing pharmacological treatments of any kind (concomitant medications) will be documented in the annotations section of the e-CRF. During the study, systemic and topical analgesic medications may be used in case of severe pain. Investigators will explain to enrolled subjects that such medications should only be used if absolutely necessary and will provide each subject with 1 package of oral analgesic medication and 1 package of topical analgesic medication among those permitted (see table 1), explaining the possible adverse events associated with intake or application and ensuring, under their responsibility, that the subject can take or apply the provided medication. To monitor its consumption, each subject will be given a clinical diary in which to record the day and dose of medication used, reminding them that such medications should not be taken or applied within 24 hours before each visit.

PERMISSIBLE ORAL MEDICATIONS	PERMISSIBLE TOPICAL MEDICATIONS
Paracetamol 1000 mg. cpr.	Diclofenac 2% gel
Etoricoxib 60 mg. cpr.	

Tab. 1 Permissible topical analgesic medications

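### The washout for earlier joint injections covers hyaluronic acid but not the marketed study device or other collagen, so recently treated subjects can enter a single-arm responder analysis

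*Protocol*

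**What the plan says.** Section 4.7.2 has one exclusion that names an earlier injection: "Subjects who have received HA injections in the thumb carpometacarpal joint in the last 3 months". The synopsis matches it: "Subjects who have received HA infiltrations in the trapeziometacarpal joint in the last 3 months". A separate exclusion reads "Subjects who have taken NSAIDs in the last 7 days and/or corticosteroids in the last 30 days" and gives no route for the corticosteroid. Collagen appears once in the list, as "Subjects allergic to porcine collagen". The last item is discretionary: "Any condition that, in the investigator's judgment, recommends the subject's exclusion".

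Other sections show that earlier exposure is possible:

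- The synopsis calls the study "Phase IV post market", and section 4.10 describes the device as already marketed.
- Section 3.3 reports, from limited case series, that "the use of type I collagen at the joint and peri-articular level in this condition is able to control painful symptoms".
- Section 4.9.2 sets the source of subjects: "During routine clinical practice, the Investigators participating in the Clinical Investigation will select subjects diagnosed with symptomatic thumb carpometacarpal osteoarthritis".

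Section 4.7.1 requires a VAS of at least 5, rated for hand use. Section 5.1.3 defines the primary result as the fraction with a VAS fall of at least 30% at week 6. Section 5.1 tests that fraction against a 20% rate of spontaneous improvement.

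**The concern.** The protocol accepts that recent local treatment can confound the change from T0 to T6: it sets three months for hyaluronic acid and three months for several physical therapies. It also measures the device's own effect at week 16. The last infiltration is at week 4 (section 4.9.1), so that is twelve weeks later, as sections 4.3 and 4.9.2 say (the synopsis says ten). The plan thus treats an effect lasting about three months as worth looking for, yet sets no interval since an earlier course of the same device.

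This matters more here than in a controlled trial, because no parallel group shares the bias. The 20% null describes spontaneous change, and a subject recently treated with collagen does not clearly fit that description. Two influences pull in opposite directions:

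- **Downward.** A subject with residual benefit has part of the effect already in the baseline, and a subject who failed an earlier course may fail again.
- **Upward.** If subjects who did well before are chosen or come forward for another course, the sample is enriched with likely responders.

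In either case the fraction no longer describes one five-injection course in a clearly defined population.

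**Working it through.** **1. Is a recent collagen recipient eligible?** Take a subject who finished a collagen course in the same thumb a few weeks ago, has VAS of at least 5 in hand use and meets the other inclusion criteria.

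- Hyaluronic acid exclusion: does not apply.
- NSAID and corticosteroid exclusion: does not apply.
- Collagen allergy: does not apply.
- Investigator's judgement: allows exclusion, does not require it.

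The subject can be enrolled.

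**2. Reproduce the plan's design (section 5.1).** Inputs: N = 33, null 0.20, alternative 0.50, rejection at 12 or more successes, lower limit at 1 or fewer.

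- Upper tail: P(X ≥ 12 | 33, 0.20) = 0.0216.
- Lower tail: P(X ≤ 1 | 33, 0.20) = 0.0059.
- Sum: 0.0275, the stated 2.75%.
- Power: P(X ≥ 12 | 33, 0.50) = 0.9599, close to the stated 95.99%.
- Recruitment: 33 / 0.8 = 41.25, rounded up to 42.

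The design figures are right. The point concerns who enters, so no corrected sample size follows from it.

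**3. Illustrate the sensitivity.** Let f be the share of previously treated subjects and r their response rate. Both are assumptions, since the protocol gives neither. If the others respond at p, the overall rate is (1 − f) × p + f × r, and the chance of crossing the rule is P(X ≥ 12 | 33, overall rate).

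Upward case, others at 0.20:

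| f | r | Overall rate | P(X ≥ 12) |
|---|---|---|---|
| 0 | – | 0.200 | 2.2% |
| 0.05 | 0.5 | 0.95 × 0.20 + 0.05 × 0.5 = 0.215 | 3.6% |
| 0.05 | 0.7 | 0.95 × 0.20 + 0.05 × 0.7 = 0.225 | 5.0% |
| 0.10 | 0.5 | 0.90 × 0.20 + 0.10 × 0.5 = 0.230 | 5.8% |

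Downward case, others at 0.50 and previously treated subjects at an assumed 0.1:

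| f | Overall rate | Power |
|---|---|---|
| 0 | 0.500 | 96.0% |
| 0.10 | 0.90 × 0.50 + 0.10 × 0.1 = 0.460 | 90.2% |
| 0.20 | 0.80 × 0.50 + 0.20 × 0.1 = 0.420 | 79.6% |

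For scale, 5% of 33 is 1.65 subjects and 10% is 3.3. A few subjects are enough to move the operating characteristics, in a direction that depends on who they are.

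**The case against.** The strongest reply is that nothing in the protocol shows such subjects will turn up. Earlier collagen use in this condition is described as limited, and no section says that either centre already injects the device or sees patients returning for a further course. This stands: the frequency is unknown, and so is whether returning patients would be past responders.

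The baseline floor also helps. A subject with large residual benefit would probably score below 5 and be screened out, and because the endpoint is a relative fall, the required drop scales with the baseline. This weakens the carry-over route without closing it, and does nothing about selection of earlier responders.

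The upward calculation can be challenged too. If previously treated subjects respond because the device works in them, crossing the threshold reflects a real effect in a subgroup, and the problem is generalisability rather than a false positive. That is fair, and is one reason to read the tables only as illustration.

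Three stronger readings are tempting and not supported:

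- **A large inflation of the false-positive rate.** A 30% share responding at 70% would give an overall rate of 0.35 and a 50.0% chance of crossing the rule. Both inputs would be guesses at a high value, so this is not an estimate for this trial.
- **No means of identifying these subjects.** Table 2 requires a medical history at T0, and section 4.9.2 has previous pharmacological treatments noted in the e-CRF. An earlier course may well appear there. What the protocol lacks is a dedicated field, and a device need not be recorded as a pharmacological treatment.
- **Every injection other than hyaluronic acid is uncovered.** The 30-day corticosteroid exclusion states no route and can be read to include steroid injections.

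**Conclusion.** The point holds as an eligibility gap. The written criteria admit a recent recipient of the study device or other collagen, while the plan applies a three-month interval to hyaluronic acid and looks for its own device's effect over a similar time. Investigator judgement permits exclusion but does not secure it, and the two centres may use it differently.

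The responder fraction can be distorted, but neither size nor direction can be derived from the protocol. On assumed small shares (5% to 10%) and rates (50% to 70% at a 5% share, 50% at a 10% share), the chance of 12 or more successes when the others are at 20% rises from 2.2% to between 3.6% and 5.8%. On an assumed low rate of 10% in previously treated subjects, power falls from 96.0% to 90.2% at a 10% share. If such subjects are rare, the effect is negligible. The change is worth making because it is cheap and must be settled before enrolment.

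**What to change.** 1. In section 4.7.2 and the synopsis, extend the hyaluronic acid criterion to collagen and other non-corticosteroid infiltrations of the trapeziometacarpal joint. Use the window the plan already applies to hyaluronic acid, with the sponsor to confirm that it suits collagen, since the protocol gives no basis for a collagen-specific interval. Leave the corticosteroid criterion as it is.
2. Add a dedicated T0 e-CRF field for any earlier collagen treatment of the study thumb, with its date. A three-month window does not remove subjects who responded to a course before that, so the first change alone does not deal with selection.
3. Report the primary fraction, with its Clopper-Pearson interval, also in collagen-naive subjects as a sensitivity analysis.

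The cost is one reworded criterion in two places, one e-CRF field and one extra table. A few otherwise eligible subjects are lost or delayed. The sample size and decision rule do not change.
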